9.4.2.1 Primary Efficacy Analyses

Primary Estimand: The primary estimand is treatment difference between VVN461 (1.0% or 0.5%) and the Vehicle in the proportion of subjects with ACC Grade 0 at Visit 6 (Day 14) in the study eye using the FAS.

Target Population: Subjects undergoing routine cataract surgery who meet the study entry criteria.

Endpoint: Proportion of subjects with ACC Grade 0 in the study eye at Visit 6 (Day 14).

Treatment Condition: Treatment condition is based on randomized treatment.

Population-Level Summary: The difference in proportions in subjects with ACC Grade 0 in the study eye at Visit 6 (Day 14) and the corresponding p-value.

Intercurrent Events and Strategies to Address Intercurrent Events

- Discontinuation of study therapy with continued participation in the study without receipt of rescue therapy
 - Treatment Policy Approach – no imputation; use observed data
- Receipt of rescue therapy (topical corticosteroid) in the study eye
 - Composite Approach – subjects who receive rescue therapy at or before the assessment visit will be assumed to have failed the primary endpoint
- Missing data with or without withdrawal, regardless of reason
 - Hypothetical Approach – no imputation; analysis will be based on subjects who have an evaluable anterior chamber in the study eye at Visit 6 (Day 14)

Pearson's chi-square will be used to test the primary endpoint between the 2 different doses of VVN461 vs the Vehicle. The primary analysis will also be performed on the PP Analysis Set.

CONFIDENTIAL

9.4.2.2 Secondary Efficacy Analyses

The secondary efficacy endpoints will include the proportion of subjects with ACC Grade 0, the proportion of subjects with ACF Grade 0, and the proportion of subjects requiring rescue medication. These endpoints will be analyzed regardless of the significance of the primary endpoint analysis.

9.4.3 Safety Analyses

Safety analyses will be performed on all subjects in the SAF. The assessment of safety will be based on the summary of ocular and non-ocular AEs, BCVA, and ophthalmic examinations using slit lamp biomicroscopy and dilated ophthalmoscopy. Summaries will be provided by treatment group and, for ocular assessments, separately by eye.

9.4.3.1 Adverse Events

AEs will be coded using MedDRA and categorized by system organ class using preferred terms. Separate summaries of AEs related to treatment (as reported by the Investigator) and by severity will be presented. The number of deaths and SAEs will also be presented, and events leading to discontinuation from the study will be listed and tabulated.

9.4.3.2 Clinical Laboratory Tests

There will not be any analysis of clinical laboratory data. Urine pregnancy tests will be conducted at Visit 1 (Screening), Visit 2 (Day of Surgery; Day 0), Visit 6 (Day 14), and Visit 7 (Day 21) for WOCBP. Results of urine pregnancy tests will be presented in a listing.

9.4.3.3 Other Safety Evaluations

Summary statistics for observed and CFB for BCVA and IOP will be presented. Abnormalities in slit lamp biomicroscopy and dilated ophthalmoscopy will be summarized by frequency and percentage. The frequency and proportion of subjects treated with rescue medications will be summarized.

Heart Rate and Blood Pressure

Heart rate and blood pressure will be assessed during screening. These measurements will be presented in a listing.

Physical Examinations

An abbreviated physical examination will be conducted during screening. The results will be shown in a listing.

CONFIDENTIAL

9.5 Interim Analysis

No interim analysis is planned for the study.

9.6 Subgroup Analyses

Subgroup analyses may be conducted based on baseline subject characteristics on a *post hoc* basis.

9.7 Exploratory Analyses

Exploratory endpoints will be analyzed in a manner similar to the secondary endpoints. Mean CFB in ACC Grade and ACF Grade will be analyzed using mixed model repeated measures. The model will include treatment, visit, and treatment by visit interaction as fixed effects and a covariate for baseline measurement (where appropriate) with a random effect for site. An unstructured covariance among repeated measurements will be assumed. Only data from before the use of rescue medication will be included in these analyses. The proportion of subjects with no post-operative ocular pain in the study eye at Visit 5 (Day 7) and Visit 6 (Day 14) will also be analyzed.

9.8 Missing, Unused, or Spurious Data

Missing data for continuous endpoints will be considered missing at random with the analysis using mixed model repeated measures. Otherwise, observed data will be analyzed at each visit.

9.9 Tabulation of Individual Subject Data

All data collected in the study will be presented in individual subject data listings for all subjects.

CONFIDENTIAL

10 Supporting Documentation and Operational Considerations

10.1 Regulatory Issues, Ethical Concerns, and Study Oversight

10.1.1 Informed Consent Process

10.1.1.1 Consent/Accent Documents

Consent forms describing in detail the study intervention, study procedures, and risks will be given to the subject, and written documentation of informed consent and privacy authorization will be required before starting intervention/administering IP. The written consent document will embody the elements of informed consent as described by the International Council for Harmonisation (ICH) and will also comply with local regulations.

If appropriate and required by the local Institutional Review Board (IRB), assent from the subject will also be obtained. If a subject is unable to sign the informed consent form, a legal representative may sign for them.

10.1.1.2 Consent Procedures and Documentation

Informed consent is a process that is initiated before a prospective subject agrees to participate in a clinical study, and this process continues throughout study participation. Informed consent forms will be approved by the IRB, and the subject will be asked to read and review the document. The Investigator will explain the research study to the subject and answer any questions that may arise. A verbal explanation will be provided in terms suited to the subject's comprehension of the purposes, procedures, and potential risks of the study and of their rights as a research subject. The subject will have the opportunity to carefully review the written consent form and ask questions before signing. The subject should have the opportunity to discuss the study with their family or surrogates or think about it before agreeing to participate in the study. The subject will sign and date the informed consent form before any procedures are done specifically for the study. The subject must be informed that participation is voluntary and that they may withdraw from the study at any time, without prejudice. A copy of the signed and dated informed consent form will be given to the subject for their records. The informed consent process will be conducted and documented in the source document (including the date), and the form signed and dated, before the subject undergoes any study-specific procedures. The rights and welfare of the subject will be protected by emphasizing to them that the quality of their medical care will not be adversely affected if they decline to participate in the study.

CONFIDENTIAL

10.1.2 Study Discontinuation and Closure

The study may be temporarily suspended or prematurely terminated if there is sufficient reasonable cause. Written notification, documenting the reason for study suspension or termination, will be provided by the suspending or terminating party to subjects, Investigators, funding agency (if applicable), the Sponsor, and regulatory authorities. If the study is prematurely terminated or suspended, the Investigator will promptly inform subjects, the IRB, and the Sponsor and will provide the reason(s) for the termination or suspension. Subjects will be contacted, as applicable, and be informed of changes to visit schedules.

Circumstances that may warrant termination or suspension may include, but are not limited to:

- Determination of unexpected, significant, or unacceptable risk to subjects
- Insufficient compliance with protocol requirements
- Data that are not sufficiently complete and/or evaluable
- Determination of futility

The study may resume once concerns about safety, protocol compliance, and data quality are addressed and satisfy the Sponsor, IRB, and/or FDA.

10.1.3 Confidentiality and Privacy

Subject confidentiality and privacy will be strictly held in trust by the participating Investigators, study personnel, and the Sponsor(s) and their interventions. This confidentiality will be extended to cover clinical information relating to subjects. Therefore, the study protocol, documentation, data, and all other information generated will be held in strict confidence. No information concerning the study or the study data will be released to any unauthorized third party without advanced written approval of the Sponsor.

All research activities will be conducted in as private a setting as possible.

The Study Monitor, other authorized representatives of the Sponsor, representatives of the IRB, regulatory agencies, and the pharmaceutical company supplying IP will be able to inspect all documents and records required to be maintained by the Investigator, including, but not limited to, medical records (i.e., office, clinic, or hospital) and pharmacy records for the subjects in the study. Sites will permit access to such records.

The study subject's contact information will be securely stored at each site for internal use during the study. At the end of the study, all records will continue to be kept in a secure location for as long a period as dictated by the reviewing IRB, Institutional policies, or Sponsor requirements.

Study subject research data, which is for purposes of statistical analysis and scientific reporting, will be transmitted to and stored in an electronic data capture system. This will not include the

CONFIDENTIAL

subject's contact or identifying information. Rather, individual subjects and their research data will be identified by a unique study identification number. The study data entry and study management systems used by sites and by contract research organization study personnel will be secured and password protected.

10.1.5 Clinical Monitoring

Lexitas Pharma Services, Inc., will conduct the clinical monitoring for the study. A clinical monitoring plan may be used and will describe in detail who will conduct the monitoring, at what frequency monitoring will be done, at what level of detail monitoring will be performed, and the distribution of monitoring reports.

10.1.6 Quality Assurance and Quality Control

Each site will perform internal quality management of study conduct, data, and documentation and completion. An individualized quality management plan may be developed to describe a site's quality management.

CONFIDENTIAL

Quality control procedures will be implemented beginning with the data entry system, and data quality control checks that will be run on the database will be generated. Any missing data or data anomalies will be communicated to the site(s) for clarification/resolution.

Following written Standard Operating Procedures, the monitors will verify that the clinical study is conducted, and data are generated, documented (recorded), and reported in compliance with the protocol, ICH Good Clinical Practice (GCP), and applicable regulatory requirements (e.g., Good Laboratory Practice [GLP], Good Manufacturing Practice [GMP]).

The site will provide direct access to all study-related sites, source data/documents, and reports for the purpose of monitoring and auditing by the Sponsor, and inspection by local and regulatory authorities.

10.1.7 Data Handling and Record Keeping

10.1.7.1 Data Collection and Management Responsibilities

Data collection is the responsibility of study personnel at the site under the supervision of the site's Investigator. The Investigator is responsible for ensuring the accuracy, completeness, legibility, and timeliness of the data reported.

All source documents should be completed in a neat, legible manner to ensure accurate interpretation of data.

Copies of the study visit worksheets may be provided for use as source document worksheets for recording data for each subject enrolled in the study. Data recorded in the eCRF derived from source documents should be consistent with the data recorded on the source documents.

Clinical data (including AEs, concomitant medications, and expected adverse reactions data) will be entered into an electronic data capture system provided by Lexitas Pharma Services, Inc. The electronic data capture system will be compliant with 21 CFR Part 11. The data system includes password protection and internal quality checks, such as automatic range checks, to identify data that appear inconsistent, incomplete, or inaccurate. Clinical data will be entered directly from the source documents.

10.1.7.2 Study Records Retention

Study documents should be retained for a minimum of 2 years after the last approval of a marketing application in an ICH region and until there are no pending or contemplated marketing applications in an ICH region or until at least 2 years have elapsed since the formal discontinuation of clinical development of the study intervention. These documents should be retained for a longer period, however, if required by local regulations. No records will be destroyed without advance written

consent of the Sponsor, if applicable. It is the responsibility of the Sponsor to inform the Investigator when these documents no longer need to be retained.

10.1.8 Protocol Deviations

A protocol deviation is any non-compliance with the clinical study protocol, ICH GCP, or Manual of Procedures requirements. The non-compliance may be on the part of the subject, the Investigator, or the study personnel. As a result of deviations, corrective actions are to be developed by the site and implemented promptly.

These practices are consistent with ICH GCP:

- 4.5 Compliance with Protocol, sections 4.5.1, 4.5.2, and 4.5.3
- 5.1 Quality Assurance and Quality Control, section 5.1.1
- 5.20 Non-compliance, sections 5.20.1, and 5.20.2.

It is the Investigator's responsibility to use continuous vigilance to identify and report protocol deviations. All protocol deviations must be addressed in study source documents and reported to the Sponsor and the reviewing IRB per their policies. The Investigator is responsible for knowing and adhering to the reviewing IRB's requirements.

10.1.9 Publication and Data Sharing Policy

The study will comply with the Clinical Trials Registration and Results Information Submission rule. As such, the study will be registered at ClinicalTrials.gov, and the results from the study will be submitted to ClinicalTrials.gov. In addition, every attempt will be made to publish results in peer-reviewed journals.

The institutions and Investigators participating in the study shall have no right to publish or present the results of the study without advance written consent from the Sponsor.

12.1 Appendix 1: Schedule of Procedures and Assessments

Study Period	Screening	Cataract Surgery	Treatment Period			End of Treatment	End of Study
			3	4	5		
Visit No.	1	2	3	4	5	6	7
Study Day	Day -30 to -1	Day 0	Day 1	Day 3 ± 1	Day 7 ± 1	Day 14 ± 2	Day 21 ± 2
Informed consent/Assent	X						
Inclusion/Exclusion criteria	X		X ¹				
Demographics	X						
Medical/Ocular/Surgical history	X						
Heart rate and blood pressure	X						
Abbreviated physical examination	X						
Urine pregnancy test	X	X				X	X
Prior/Concomitant medications	X	X	X	X	X	X	X
Subject administration of test eye drop	X						
Randomization			X				
Dispense IP			X		X		
Collect unused IP					X	X	
In-clinic administration of IP			X				
Pain score training	X		X				
NPRS			X	X	X	X	
Dosing adherence				X	X	X	
AE monitoring		X	X	X	X	X	X
Slit lamp biomicroscopy	X		X	X	X	X	X
BCVA	X		X	X	X	X	X
IOP	X		X	X	X	X	X
Dilated ophthalmoscopy	X						X

Abbreviations: ACC=anterior chamber cell; AE=adverse event; BCVA=best corrected visual acuity; CELR=cataract extraction and lens replacement; IOP=intraocular pressure; IP=investigational product; NPRS=Numeric Pain Rating Scale

¹Inclusion and exclusion criteria will be assessed at Visit 1 (Screening); subjects who meet eligibility requirements at Visit 1 (Screening) will continue to be eligible for study participation if they present at Visit 3 (Baseline/Randomization) with ACC inflammation ≥ 2 in the study eye after having completed CELR surgery at Visit 2 (Day of Surgery) without surgical complications.

CONFIDENTIAL

12.2 Appendix 2: Woman of Childbearing Potential (WOCBP)

Pregnancy or refusal to adhere to contraception requirements is exclusionary.

Female subjects and female partners of male subjects are considered of non-childbearing potential if they have been in menopause for at least 1 year, have had a tubal ligation at least 1 year before Visit 1 (Screening), or have had a total hysterectomy. Contraception is not required during the study for those of non-childbearing potential.

Sexually active female subjects of childbearing potential with a partner capable of fathering children must be willing to use 1 or more of the following forms of contraception from the time of signing the informed consent form for the duration of the study:

- Hormonal contraception (oral, implantable, injectable, transdermal)
- Mechanical contraception (spermicide in conjunction with a barrier method such as a condom or diaphragm)
- Intrauterine device
- Vasectomized partner(s) (6 months minimum)
- When in keeping with a subject's usual lifestyle and preferences, abstinence may also be regarded as an adequate method of birth control, where abstinence in this context is defined as refraining from any sexual activities or contact that may result in creation of a zygote.
 - **Note:** If a subject who was abstinent under this definition becomes sexually active during the study, they must agree to use acceptable contraception as defined above for the remainder of the study.

Sexually active male subjects with partners who are WOCBP must be willing to use 1 or more of the above forms of birth control for either themselves or their partner, as appropriate, from the time of signing the informed consent form for the duration of the study.

- Male subjects who underwent a vasectomy at least 6 months before Visit 1 (Screening) are not required to use any other forms of contraception during the study.

CONFIDENTIAL

12.3 Appendix 3: Slit Lamp Biomicroscopy

The slit lamp biomicroscopy examination will be performed with the slit lamp using a beam width and intensity that provides optimal evaluation of the anterior segment. The slit lamp biomicroscopy examination does not require fluorescein dye, although fluorescein dye may be used at Investigator discretion.

The slit lamp biomicroscopy examination must be performed before any procedures that would require contact with the eye and before the application of any dilating or anesthetic eye drops. The Investigator should use their standard examination technique. This procedure should be performed in the same manner for all subjects. When possible, the same Investigator should conduct all slit lamp biomicroscopy examinations at each visit for a given subject throughout the study to ensure consistent grading.

The Investigator must examine each eye (right eye first, then left eye) and record a grade for each tissue/structure listed in [Table 3](#). Observations should be recorded in the source document and logged in the appropriate eCRF.

All subjects will undergo routine cataract surgery and implantation of an intraocular lens; therefore, all subjects will change from phakic to pseudophakic. This should not be considered an AE, as it is a planned part of the study design.

Table 3 Slit Lamp Tissue/Structure Assessments

Tissue/Structure	Grade
Eyelids & Adnexa	0 = Normal; no swelling/abnormality of the eyelid tissue 1 = Abnormal Not Clinically Significant Clinically Significant If Abnormal, Clinically Significant, specify: _____
Conjunctiva Conjunctival Hyperemia Edema (Chemosis) Conjunctival Discharge/Exudate	0 = None 1 = Mild 2 = Moderate 3 = Severe
Cornea Corneal Edema	0 = None 1 = Mild 2 = Moderate 3 = Severe
Iris	0 = Normal 1 = Abnormal Not Clinically Significant Clinically Significant If Abnormal, Clinically Significant, specify: _____

CONFIDENTIAL

Tissue/Structure	Grade
Pupil	0 = Normal 1 = Abnormal Not Clinically Significant Clinically Significant If Abnormal, Clinically Significant, specify: _____
Sclera	0 = Normal; without any redness/abnormality 1 = Abnormal Not Clinically Significant Clinically Significant If Abnormal, Clinically Significant, specify: _____
Crystalline Lens Status	Phakic Pseudophakic Aphakic

The severity of ocular inflammation will be assessed by the Investigator using a slit lamp and graded using the SUN Working Group Grading Scale for the Anterior Chamber ([Table 4](#)).

Table 4 SUN Working Group Grading Scale for the Anterior Chamber

Anterior Chamber Cells		Anterior Chamber Flare	
Grade	Cells in Field ¹	Grade	Description
0	0	0	None
0.5+	1–5	1+	Faint
1+	6–15	2+	Moderate (iris and lens details clear)
2+	16–25	3+	Marked (iris and lens details hazy)
3+	26–50	4+	Intense (fibrin or plastic aqueous)
4+	>50		

Abbreviations: SUN=Standardization of Uveitis Nomenclature

¹Field size is a 1 mm by 1 mm slit beam

[figure not shown]
Reference: [Jabs et al., 2005](#)

CONFIDENTIAL

12.4 Appendix 4: Numeric Pain Rating Scale (NPRS)

Subjects will be asked at each post-operative visit, excluding Visit 7 (Day 21), to rate their ocular pain in the study eye using an 11-point NPRS scale. Subjects will be provided with pain score training to help harmonize subjective reporting across subjects and across sites.

“0” will represent no ocular pain. “10” will represent the worst ocular pain imaginable.

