7.1.5 Visit 5 (Day 7 ± 1)

The following procedures will be performed at Visit 5 (Day 7 ± 1):

- AE monitoring
- Concomitant medication update
- NPRS
- BCVA
- Slit lamp biomicroscopy
- IOP
- Collect unused IP
- Review dosing adherence and dairy entries
- Dispense IP
- Schedule or confirm next visit and remind subject to return with IP and dosing diary

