7.1.6 Visit 6 (End of Treatment; Day 14 ± 2)

The following procedures will be performed at Visit 6 (End of Treatment; Day 14 ± 2):

- AE monitoring
- Concomitant medication update
- NPRS
- BCVA
- Slit lamp biomicroscopy
- IOP
- Collect unused IP
- Review dosing adherence and dairy entries
- Urine pregnancy test (only for WOCBP)*
- Schedule or confirm next visit

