7.1.7 Visit 7 (End of Study; Early Termination; Day 21 ± 2)

The following procedures will be performed at Visit 7 (End of Study; Early Termination; Day 21 ± 2):

- AE monitoring
- Concomitant medication update
- BCVA
- Slit lamp biomicroscopy
- IOP
- Dilated ophthalmoscopy
- Urine pregnancy test (only for WOCBP)*
- Release subject from study

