7.1.9 Early Termination

In the event that a subject withdraws or is terminated from the study before the end of the study, every attempt will be made to ensure that the subject returns to the site as soon as possible and completes the Visit 7 (End of Study; Early Termination) assessments before being discharged from the study. Any unused IP should be collected during an early termination visit.

CONFIDENTIAL

8 Study Assessments

The Schedule of Procedures and Assessments ([Appendix 1](#): Schedule of Procedures and Assessment) provides a list of study assessments and evaluations to be performed and the timing of each.

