### Missing Data and Outliers

Missing data for continuous endpoints will be considered missing at random with the analysis using mixed model repeated measures. Otherwise, observed data will be analyzed at each visit.

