#### **9.7.1.5. Analysis of Efficacy**

Summary descriptive statistics will be presented for all study visits at which efficacy data are collected. Efficacy analyses will be presented by the study eye.

For subjects who discontinue treatment prior to the Visit 7, the data collected on the Early Termination eCRFs will not be summarized unless the termination within the visit windows of a particular visit.

All longitudinal models will be fit using the MIXED procedure in SAS. Categorical analyses will be conducted using the FREQ procedure.

Secondary and exploratory endpoints will be analyzed in a similar manner to the primary endpoint regardless of the significance of the primary endpoint analysis. All efficacy analyses will be conducted using the FAS and PP Analysis Sets.

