### 9.7.1.5.3. Exploratory Efficacy Analysis

Exploratory endpoints will include the proportion of subjects with no postoperative ocular pain (NPRS = 0) in the study eye at Visit 5 (Day 7) and at Visit 6 (Day 14).

Observed mean NPRS prior to rescue mediation will also be analyzed at each given visit.

The following study eye endpoints will be analyzed at each visit using a mixed model repeated measures:

- 1) Mean CFB in ACC Grade
- 2) Mean CFB in ACF Grade
- 3) Mean NPRS

The model will include treatment, visit, and treatment by visit interaction as fixed effects and a covariate for baseline measurement (where appropriate) with a random effect for site. An unstructured covariance among repeated measurements will be assumed. If the model fails to converge using this covariance structure, spatial power or compound symmetry will be implemented in this order until convergence is reached. If convergence is not reached, values will be denoted as “--”. Only data from before the use of rescue medication will be included in these analyses.

run;

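### An early-termination visit can supply cell and flare grades but no pain score, so some in-window leavers drop out of the exploratory pain-free proportions

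*Protocol*

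**What the plan says.** **What is collected.** Protocol 7.1.9 asks that a subject who leaves early comes back and "completes the Visit 7 (End of Study; Early Termination) assessments before being discharged from the study". Section 7.1.7 opens that list with "The following procedures will be performed at Visit 7 (End of Study; Early Termination; Day 21 ± 2"). It holds AE monitoring, concomitant medication, BCVA, slit lamp, IOP, dilated ophthalmoscopy and a pregnancy test. ACC and ACF are graded at the slit lamp (Appendix 3). The Numeric Pain Rating Scale (NPRS) is not on the list. Both schedules (Protocol Appendix 1, SAP Appendix I) place it at Visits 3 to 6 only, and Protocol Appendix 4 says "Subjects will be asked at each post-operative visit, excluding Visit 7 (Day 21), to rate their ocular pain in the study eye".

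**What is analysed.** For early leavers, SAP 9.7.1.5 states that "the data collected on the Early Termination eCRFs will not be summarized unless the termination within the visit windows of a particular visit". SAP 9.7.1.5.3 adds: "Exploratory endpoints will include the proportion of subjects with no postoperative ocular pain (NPRS = 0) in the study eye at Visit 5 (Day 7"), and the same at Visit 6. Under Missing Data and Outliers, the SAP treats continuous endpoints as missing at random in the repeated-measures model. For everything else, "Otherwise, observed data will be analyzed at each visit".

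**What bears on it from elsewhere.**
- SAP 9.7.1.5 has exploratory endpoints handled along the same lines as the primary endpoint.
- SAP 9.7.1.5.1 counts rescued subjects, and those who stop for lack of efficacy or an adverse event, as failures. It words these rules for the primary endpoint.
- The SAP paragraph on visit windows assigns data by the nominal CRF visit.

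**The concern.** The SAP keeps efficacy data from an early-termination visit that falls in a window, but the protocol does not collect the pain item there. One visit can then count for inflammation and be missing for pain.

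The pain-free proportion is a binary endpoint analysed as observed. A leaver with no score, and no failure rule to place him or her, is taken out of the denominator. If that subject was in pain, the arm's pain-free rate goes up, and more so in the arm with more such exits. The score cannot be recovered after discharge. Protocol 1.1 names pain alongside inflammation in the intended US use, so the pain data matter for development even though the endpoints are exploratory.

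**Working it through.** **1. The plan's own figures.** Inputs from Protocol 9.2: 30 completers per arm, 30% against 65%, two-sided 0.05, 10% drop-out.
- Power = Φ{[0.35·√30 − 1.96·√(2·0.475·0.525)] / √(0.30·0.70 + 0.65·0.35)} = Φ{(1.917 − 1.384)/0.661} = 79.0%. Exact enumeration of the Pearson test gives 79.8%, in line with the stated 80%.
- Drop-out: 30/(1 − 0.10) = 33.3, rounded up to 34 per arm; 3 × 34 = 102, as stated.

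Nothing here disputes these figures. They supply the expected number of leavers: 0.10 × 34 = 3.4 per arm (34 − 30 = 4 after rounding).

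**2. The windows.** Section 7.1.5: "The following procedures will be performed at Visit 5 (Day 7 ± 1"), so Days 6-8, which is 3 days. Section 7.1.6: "The following procedures will be performed at Visit 6 (End of Treatment; Day 14 ± 2"), so Days 12-16, which is 5 days. Visit 4 (Day 3 ± 1) covers Days 2-4. Of the 15 days from Day 2 to Day 16, Days 5, 9, 10 and 11 lie in no window.

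**3. Where the mismatch arises.**

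| Early-termination visit on | ACC/ACF usable for | Pain score scheduled |
|---|---|---|
| Days 2-4 | Visit 4 | no |
| Days 6-8 | Visit 5 | no |
| Days 12-16 | Visit 6 | no |
| Days 5, 9-11 | no visit | no |

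The pain-free proportions are defined at Visits 5 and 6, so only Days 6-8 and 12-16 matter for them. An exit on Days 6-8 supplies no Day 14 grade either, so there is no mismatch at Visit 6 for that subject.

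**4. Subjects affected per arm.** Assumption: exits are spread evenly over Days 2-16.
- Visit 5: 3.4 × 3/15 = 0.7
- Visit 6: 3.4 × 5/15 = 1.1

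With 4 leavers in place of 3.4, these become 0.8 and 1.3. All lean high: they assume that each leaver attends the early-termination visit, is not already counted as a failure, and has not already had that visit's pain rating.

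**5. Effect on one proportion.** The documents give no pain-free rate; 15/34 is an assumption.
- One subject in pain removed: 15/34 = 44.1% becomes 15/33 = 45.5%, up 1.3 points.
- One pain-free subject removed: 14/33 = 42.4%, down 1.7 points.

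**6. Outer bound.** If all 4 planned drop-outs in an arm had no score, an assumed observed 18/30 = 60.0% could stand for anything from 18/34 = 52.9% to 22/34 = 64.7%. Most of that width comes from exits outside the window in question, which a pain question at the early-termination visit would not repair.

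**The case against.** The strongest reply is that the harmful case may already be covered. A subject who leaves because the eye hurts would plausibly be recorded as rescued, or as stopping for lack of efficacy or an adverse event. If the primary endpoint's failure rules carry over, that subject counts as not pain-free without any score. SAP 9.7.1.5 points that way. This limits the concern but does not remove it. SAP 9.7.1.5.1 names only the primary endpoint. Exits recorded as withdrawal of consent or investigator decision fall outside the rules. Lack of efficacy is not among the withdrawal reasons in Protocol 6.2, although that list is open-ended.

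Other points that stand:
- Earlier scores are kept. A subject who leaves after Visit 5 stays in the Day 7 proportion, and earlier scores stay in the model for mean NPRS. That model relies on missing at random, which is doubtful if new pain prompted the exit.
- The SAP refers to the window of a visit in general and does not single out Visits 5 and 6. Its nominal-visit rule points the other way.
- Appendix 4 excludes Visit 7 at Day 21, which does not plainly cover an earlier early-termination visit. Protocol 7.1.8 leaves efficacy assessments at unscheduled visits to the investigator. Neither forbids a pain score, but a site following 7.1.7 will not take one.

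A reader might infer that early leavers as a class drop out of the pain endpoints by rule. The documents do not support that: failure rules may apply, earlier scores remain, and the mismatch exists only inside a window. A reader might also pool the two windows (3.4 × 8/15 = 1.8) and take two subjects off one endpoint, giving 15/32 = 46.9%, close to 3 points. No single endpoint loses that many under the same assumption.

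**Conclusion.** The point holds in a limited form. An in-window early-termination visit supplies ACC and ACF but no scheduled pain score. A leaver not covered by a failure rule is then missing from the pain-free proportion at that visit. The size is about 0.7 subject per arm at Visit 5 and 1.1 at Visit 6, or about 1.3 points for one subject in pain. This rests on the plan's 10% drop-out, an even spread of exits over Days 2-16, and an assumed 15/34 pain-free rate. It would be larger if exits cluster in a window.

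A bias between arms is possible but not shown. Similar exits in each arm would largely cancel, and the sign depends on whether those leaving are in pain. The primary and secondary endpoints and the sample size are untouched, and the pain p-values are nominal by the SAP's own statement. This is a cheap improvement to data collection, together with a clarification the SAP needs.

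**What to change.** 1. **Protocol 7.1.7, 7.1.9, Appendix 1 and Appendix 4:** add the NPRS to early-termination visits held up to the end of the Visit 6 window (Day 16). Place it after AE monitoring and the concomitant medication update and before BCVA, as at Visits 4 to 6.
2. **SAP 9.7.1.5.1 and 9.7.1.5.3:** state whether the failure rules for rescue, lack of efficacy and adverse events apply to the pain-free proportions.
3. **SAP 9.7.1 (Visit Windows) and 9.7.1.5:** reconcile the nominal-visit rule with the window-based use of early-termination data, and give the windows in days.

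The cost is one question and one eCRF field at a visit that already takes place, plus a few sentences in the SAP. Scores taken on Days 5 or 9-11 would reach the listings only, since they fall in no window.
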